## INTRODUCTION

Multifocal (MF) and multicentric (MC) breast cancers are relatively common clinical entities, with incidence in the literature ranging from 6% to 60%. This large variability is due to differences in definitions used, inclusion or exclusion of *in situ* disease, and methods of pathologic sampling. Most commonly, MF breast cancer typically refers to two or more synchronous areas of disease confined within the same quadrant versus MC disease, which refers to two synchronous areas of disease within different quadrants. Regardless of the definition, the tumor with the greatest diameter is typically used for staging purposes.

As advances in preoperative imaging continue, the number of MF and MC tumors identified increases, and better guidelines for their management are needed. In particular, questions still exist regarding the optimal loco-regional (LR) therapy for MF and MC breast cancer. Multifocality and multicentricity are regularly considered as a relative contraindication for breast-conservation therapy. The reasoning for this traditional paradigm is based on two assumptions. **Firstly**, the perceived higher risk for in-breast recurrence since it is assumed that in MF/MC cancer the risk of more invasive foci in the breast is greater, and therefore radiotherapy possibly less effective. **Secondly**, the expected less good cosmetic outcome due to wide excisions and larger boost volumes with more fibrosis. Consequently, the vast majority of patients with MF/MC, either clinically detected or visible on standard imaging (mammography, ultrasound) is advised to be treated with a mastectomy. However, such a tendency towards a more extensive surgery is debated. The COMICE trial did not show any reduction of local recurrence or any improvement of long-term survival in patients undergoing preoperative MRI.

Three more recent developments may change this traditional paradigm.

جامعة

**First**, the introduction of MRI has led to the identification of more small cancer foci besides the index cancer.

**Secondly**, more effective neo-adjuvant chemotherapy result in more complete or near complete remissions or substantial reductions in the extent of cancers. **Thirdly**, improved surgery by better localization techniques and oncoplastic procedures allow for more precise and complete breast conserving resections.

Furthermore, Multifocal/MC disease has also been implicated as a prognostic factor. Studies have demonstrated that MF/MC cancers may have an increased susceptibility to axillary lymph node (LN) involvement. It is unclear whether this is due to inaccurate staging by using the largest tumor dimension or if these malignancies have an inherent biologic capacity to spread.

In addition, MF/MC disease has been found to correlate with known risk factors suggesting an aggressive biology such as young age, higher grade, negative hormone receptor status, negative HER-2 status, and lymphovascular invasion. Yet the impact on outcomes is unclear with studies demonstrating mixed results.

Unfortunately, due to the relatively heterogeneous cohort of patients with MF/MC breast cancer, standardized guidelines are not well established.

Therefore, it remains unclear whether MF/MC breast cancers should be considered a separate category with a potentially unfavourable impact on prognosis and whether these lesions require specific treatment with more extensive surgery or committed adjuvant therapies.

[name]

[figure not shown]
✓

✓

✓

The present study is directed to analyze, in a large retrospective series of breast cancer patients treated at a single institution, the impact of (MF) breast cancers on the long-term survival in relation to other known pathological and clinical factors and to the type of treatment received. Furthermore, the prospective limb of this study is directed to evaluate the outcomes of oncoplastic techniques as a surgical management for multifocal breast cancer.

[name]

## AIM OF THE WORK

[figure not shown]
This work aims to:

**Primary objective:**

Evaluating the application of oncoplastic surgical techniques in the surgical treatment of multifocal breast cancer as regards; successful resection of tumor burden, disease control (recurrence) and cosmetic results.

**Secondary objectives:**

1. Determine the burden of multifocal breast cancer among Egyptian population.
2. Determine to what extent the presence of (MF) is associated with the use of mastectomy.
3. Determine the factors that are associated with the use of BCT in the presence of (MF) disease.
4. Determine whether the presence of (MF) increased the rate of local relapse in patients treated with BCT.
5. Exploring the association between multifocality and overall survival and loco-regional relapse.
6. Stating a reliable recommendations for management of multifocal breast cancer.

Handwritten signatures and initials are present at the bottom of the page, including a signature in Arabic and a signature in English.

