## PATIENTS

This study includes two groups of patients:

**Group (A):** All patients with operable breast cancer , admitted and managed at the Surgical Oncology unit, Alexandria Faculty of Medicine, between Jan.2010 to Dec.2015, their data are retrospectively reviewed and analyzed.

**Group (B):** All patients with operable multifocal breast cancer excluding those indicated for neoadjuvant therapy and those diagnosed as inflammatory breast cancer admitted between May.2017 to May.2018 will be offered oncoplastic breast conserving surgery and prospectively evaluated for 24 months as regards the outcomes of using different oncoplastic techniques to extend the clinical utility of BCT as a surgical management for multifocal breast cancer.

[name]

الدكتور

[name]

الدكتور

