## METHODS

**For group (A) patients The following data of will be included and recorded:**

- Age at diagnosis: young patients are defined as younger than 35 years.
- Surgery performed:
  - a-Breast conservation: involves lumpectomy with oncologically appropriate safety margins with either sentinel lymph node detection or axillary lymph node dissection according to the triple assessment of the patients. The introduction of different oncoplastic procedures in breast cancer surgery allows more breast conservation.
  - b-Mastectomy: modified radical mastectomy.
- Tumor characteristics: size, nodal status, presence of lympho-vascular invasion, amount of intraductal component, tumor grade, margin status, hormone receptor, and Her2 neu status(if available).
- Pathological determination of multifocal and unifocal tumors.
- The follow-up period of the patients was registered.
- The occurrence of loco-regional recurrence or distant metastases during the follow-up period was recorded and considered as an end point for follow-up.

Local recurrence is defined as recurrence in the original tumor bed (for BCS) or field of mastectomy.

Regional recurrence refers to metastatic disease in the ipsilateral axilla or supraclavicular lymph nodes or ipsilateral involvement of internal mammary nodes.

Loco-regional recurrence-free survival of patients who are pathologically multi-focal and uni-focal will be estimated using the Kaplan-Meier method and compared among different categories using log-rank tests (univariable analysis

in 4/12

([name])

of risk factors for loco-regional recurrence among multi-focal and uni-focal breast cancer patients).

Distal recurrence-free survival for both groups will be analyzed using the same test (univariable analysis of risk factors for distal recurrence).

Associations with local recurrence in uni-focal and multi-focal breast cancer patients are further evaluated using multivariable Cox proportional hazards regression model and summarized with hazard ratios 95 % confidence intervals (CIs).

Associations with distal recurrence uni-focal and multi-focal breast cancer patients will be further evaluated using multivariable Cox regression model.

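### Secondary objective 1 promises the burden of multifocal breast cancer in Egypt, but the design can give only a proportion among operable cases at one surgical unit

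*Protocol*

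**What the plan says.** The Protocol, under Secondary objectives, item 1, sets out to "Determine the burden of multifocal breast cancer among Egyptian population". It does not say whether burden means incidence, prevalence or a share of cases.

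The Patients section describes two groups:

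- **Group A** is "All patients with operable breast cancer , admitted and managed at the Surgical Oncology unit, Alexandria Faculty of Medicine, between Jan.2010 to Dec.2015", reviewed retrospectively. The Introduction describes the retrospective part as being carried out "in a large retrospective series of breast cancer patients treated at a single institution".
- **Group B** is "All patients with operable multifocal breast cancer excluding those indicated for neoadjuvant therapy and those diagnosed as inflammatory breast cancer", admitted from May 2017 to May 2018.

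For Group A, the Methods list "Pathological determination of multifocal and unifocal tumors" among the data to be recorded and add no working definition. The Introduction says what multifocal and multicentric usually mean. It attributes the published range of 6% to 60% to differing definitions, the handling of in situ disease, and pathologic sampling.

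The SAP's descriptive analysis consists of frequencies and percentages. The only confidence intervals in either document are those for hazard ratios in the Group A recurrence models.

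**The concern.** The objective names a national population, while the data come from one unit and one type of patient. The Protocol's Discussion section says the results will be discussed in view of whether the aim was achieved, so the wording of the aim governs how the percentage will be presented. Followed as written, the plan would attach a national label to a unit-level percentage. Enrolling more patients or adding an interval would not cure this, because the gap lies in who was sampled and not in how many.

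**Working it through.** The documents give no sample size, expected proportion or precision target for this objective, so there is no planned figure to reproduce. The check compares what the objective needs with what the plan provides.

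| Needed for the stated objective | What the plan provides |
|---|---|
| A denominator of people, if burden means incidence or prevalence | None; only cases are recorded |
| Cases from across Egypt, if burden means a share of cases | One unit (Protocol, Introduction and Patients) |
| Operable and inoperable cases | Operable only, in both groups |
| Multifocal and unifocal cases in one series | Group A only; Group B enrols multifocal cases alone, so its multifocal share is 100% by construction |
| A step from sample to population (weighting, standardisation, registry linkage) | None in the Protocol or SAP |
| A fixed definition of multifocality | Pathological determination, not defined in the Methods |

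**The gap in symbols.** Read burden in the way most favourable to the plan, as a share of cases. Let s be the share of Egyptian breast cancers that the unit's operable series represents, p_unit the multifocal proportion in that series, and p_other the proportion among all remaining cases. Then:

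- national proportion = s × p_unit + (1 − s) × p_other
- national proportion − p_unit = (1 − s) × (p_other − p_unit)

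The study will observe p_unit. The documents give neither s nor p_other and plan no data on either. The sign of the difference is that of p_other − p_unit, which is unknown. With nothing assumed about p_other, the national proportion can lie anywhere from s × p_unit to s × p_unit + (1 − s), an interval of width 1 − s. Because s is unknown, no numerical bound follows.

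**What an interval would and would not cover.** Sampling error can be illustrated with the 95% half-width 1.96 × √(p(1 − p)/n). The values of n are assumptions, as is p = 20%; 6% and 60% are the ends of the range cited in the Introduction.

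| n (assumed) | p = 6% | p = 20% | p = 60% |
|---|---|---|---|
| 200 | ±3.3 points | ±5.5 points | ±6.8 points |
| 500 | ±2.1 points | ±3.5 points | ±4.3 points |
| 1000 | ±1.5 points | ±2.5 points | ±3.0 points |

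For example, at p = 20% and n = 500: 1.96 × √(0.20 × 0.80/500) = 0.035.

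The Wilson form proposed below behaves similarly. For an assumed 75 of 500 (15%), the centre is (0.15 + 3.8416/1000)/(1 + 3.8416/500) = 0.1527. The half-width is 1.96 × √(0.15 × 0.85/500 + 3.8416/(4 × 500²))/(1 + 3.8416/500) = 0.0313. The interval is 12.1% to 18.4%.

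These widths shrink as n grows. The term (1 − s) × (p_other − p_unit) does not contain n.

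**The case against.** The best defence is that this is loose wording in a minor place. The item is one of six secondary objectives, is purely descriptive and has no hypothesis test. The Introduction openly says the series comes from one institution, so a reader can judge its scope. Neither document contains conclusions, so a national claim in the final report is a prediction.

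Most of this is fair, and it limits the weight of the point. It does not remove the point. The objective is the only statement of what is to be estimated, nothing elsewhere narrows it, and disclosing the source does not supply the missing step to the population.

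A reader might also infer several stronger things that the documents do not support:

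- *That the national proportion is higher than the unit's.* Neither document says that multifocality is commoner, or rarer, among inoperable patients or those treated elsewhere.
- *That a corrected national figure can be worked out.* This needs the unit's share of Egyptian cases, which is not given. Treating operable cases at this unit as if they were all operable cases in Egypt would be a further unsupported step.
- *That the unit is a referral centre with a known selection pattern.* The Protocol calls it a surgical oncology unit of a faculty of medicine and says nothing about referral.
- *That the 6% to 60% range measures the selection error.* The Protocol attributes that range to definitions, in situ disease and sampling, for multifocal and multicentric disease together. It supports fixing a definition and says nothing about who was sampled.

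**Conclusion.** The mismatch is real and can be read directly from the Protocol. Group A can support the proportion of pathologically multifocal tumours among operable cases managed at that unit in 2010–2015. It cannot support an incidence or prevalence, because there is no denominator of people. Nor can it support a national share of cases, because other centres and inoperable cases are absent and nothing links the unit to the country. Neither the size nor the direction of any difference from the national figure can be estimated, and this conclusion does not rest on any of the assumed numbers above.

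The consequence is limited to what may be concluded from one secondary, descriptive objective. A reader might infer that the primary objective or the recurrence comparisons are undermined. They are not, since neither uses this proportion. The change should be made, but the study does not hang on it.

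**What to change.** Restate secondary objective 1 along these lines:

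> The proportion of pathologically multifocal tumours among operable breast cancers managed at the Surgical Oncology unit, January 2010 to December 2015, with a 95% Wilson confidence interval. Multifocal means at least two synchronous foci within one quadrant; the handling of in situ and multicentric disease is to be stated.

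The definition follows the usage that the Protocol's Introduction describes as most common. It has to be written into the Methods, because the restated proportion is ambiguous without it. Add the interval to the SAP's descriptive section, noting that it reflects sampling error only, and do not report the result as an Egyptian population burden.

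The cost is a change of wording, a definition and one interval. No new patients are needed and clinical management is unaffected. The downside is a less ambitious claim. Keeping the national objective would require a population-based source, which neither document provides.

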**Tailoring Surgical Management of Multifocal
Breast Cancer:is There a Possibility**

NCT03900299

Document Date: December 2, 2019

Data Management and Analysis:

The collected data was revised, coded, tabulated and introduced to a PC using Statistical package for Social Science (**IBM Corp. Released 2011. IBM SPSS Statistics for Windows, Version 20.0. Armonk, NY: IBM Corp.**). Data was presented and suitable analysis was done according to the type of data obtained for each parameter as follow :.

I-Descriptive statistics:-Frequency and percentage of qualitative variables.

II-Analytical statistics:

1. Chi-Square test was used to examine the relationship between two qualitative variables

2. Fisher's exact test: was used to examine the relationship between two qualitative variables for 2x2 tables (tables with 4 cells), when the expected count is less than 5 in more than 20% of cells

3-Monte Carlo-test was used to examine the relationship between two qualitative variables for larger than 2x2 tables (tables with more than 4 cells) when the expected count is less than 5 in more than 20% of cells

- P- value: level of significance

-P>0.05: Non significant (NS).

-P< 0.05: Significant (S).

-P<0.01: Highly significant (HS).

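### No adjusted analysis is specified for choice of operation (secondary objectives 2 and 3), and no effect measure is named for the two-variable tests that are listed

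*Protocol*

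**What the plan says.** Two of the protocol's secondary objectives have choice of operation as the outcome. Objective 2 is to "Determine to what extent the presence of (MF) is associated with the use of mastectomy". Objective 3 is to "Determine the factors that are associated with the use of BCT in the presence of (MF) disease".

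The natural population for both is Group A, the 2010-2015 series for whom "their data are retrospectively reviewed and analyzed" (Patients section). Group B patients are all to be offered oncoplastic conservation, so they give no planned comparison of operations. For Group A the Methods section records age, operation and "Tumor characteristics: size, nodal status, presence of lympho-vascular invasion, amount of intraductal component, tumor grade", then margin status, hormone receptors and, if available, HER2.

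The SAP's analytical section begins "Chi-Square test was used to examine the relationship between two qualitative variables". It adds Fisher's exact test for sparse 2x2 tables and, for sparse larger ones, "Monte Carlo-test was used to examine the relationship between two qualitative variables for larger than 2x2 tables". It then gives P-value cut-offs for significance labels. It names no effect measure, confidence interval or regression model.

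The protocol's Methods section for Group A does plan adjusted analysis, but for recurrence: associations with local recurrence are "further evaluated using multivariable Cox proportional hazards regression model and summarized with hazard ratios", and distal recurrence also gets a multivariable Cox model.

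**The concern.** Group A is a non-randomised series. The Introduction says that multifocal or multicentric disease correlates with younger age, higher grade, receptor and HER2 negativity, and lymphovascular invasion, and may carry more nodal involvement. The Methods section remarks that the introduction of oncoplastic procedures allows more conservation, so calendar time may matter too. If such factors also relate to the operation chosen, a two-way table mixes their contribution with that of multifocality.

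Objective 3 is the more exposed. It asks for a set of factors, and those factors are likely to be related to one another. Testing each alone can label several as significant for one underlying reason, with no means of telling which carries independent information.

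For objective 2 there is a second gap. It asks about extent, and a test statistic with a significance label does not supply one.

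Objective 6 is to derive recommendations for managing multifocal disease. A crude association could enter those recommendations as if it were the effect of multifocality itself.

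**Working it through.** **What the plan covers.** The documents state no sample size, event count or effect size for objectives 2 and 3, so there is no figure to reproduce. Set side by side, the planned analyses are:

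- Loco-regional and distal recurrence: Kaplan-Meier, log-rank, then multivariable Cox (protocol, Methods, Group A).
- Mastectomy against BCT by focality (objective 2): no method named; of those listed, only the SAP's frequencies and two-variable tests fit a binary surgical outcome.
- Factors for BCT within multifocal disease (objective 3): the same.

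So recurrence gets the step from univariable to multivariable analysis, and choice of operation does not. Most of the variables needed are on the protocol's own recording list.

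**How large a crude association could arise with no effect of multifocality.** Every rate here is assumed. Tumour size stands in for any confounder. Let q be the share of large tumours in a group, and m_L and m_S the mastectomy rates in large and small tumours, taken as identical in multifocal and unifocal patients, so that the size-adjusted OR is 1.0.

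- Group rate: p = q × m_L + (1 − q) × m_S
- Crude OR = [p_MF / (1 − p_MF)] / [p_UF / (1 − p_UF)]

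Assumed ranges: q = 45-60% (multifocal) and 30-35% (unifocal); m_L = 80-85%; m_S = 45-50%.

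*Lowest corner* (45% v 35% large; mastectomy 80% and 50%):
- p_MF = 0.45 × 0.80 + 0.55 × 0.50 = 0.635
- p_UF = 0.35 × 0.80 + 0.65 × 0.50 = 0.605
- OR = (0.635/0.365) / (0.605/0.395) = 1.14

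*Highest corner* (60% v 30% large; mastectomy 85% and 45%):
- p_MF = 0.60 × 0.85 + 0.40 × 0.45 = 0.690
- p_UF = 0.30 × 0.85 + 0.70 × 0.45 = 0.570
- OR = (0.690/0.310) / (0.570/0.430) = 1.68

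*Equal size mix:* p_MF = p_UF, so OR = 1.00 and there is no bias.

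**How often the unadjusted test would then be significant.** A second assumed set takes mastectomy rates of 80% (large) and 40% (small), and again no multifocal effect. Probabilities are for P<0.05, two-sided (the SAP does not state sidedness).

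| Large tumours, MF v unifocal | Crude mastectomy rate | Crude OR | 100 v 500 patients | 200 v 1000 patients |
|---|---|---|---|---|
| 60% v 40% | 64% v 56% | 1.40 | 31% | 55% |
| 60% v 30% | 64% v 52% | 1.64 | 60% | 88% |

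**Objective 3.** The same algebra applies within multifocal patients if focality is replaced by any factor that is related to size but has no association of its own with the operation. With the first set of ranges, its crude OR for BCT would be the inverse, 1/1.14 = 0.88 to 1/1.68 = 0.60. Testing that factor and size separately could flag both; a joint model is needed to tell them apart.

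**The case against.** The strongest reply concerns objective 2. As worded it asks about association and makes no claim of independence or cause. The proportions having mastectomy in multifocal and unifocal patients, which the SAP's frequencies and percentages would supply, answer it on that reading and show extent in a crude way. The Introduction also says that multifocality is itself regularly treated as a relative contraindication to conservation, so a crude association is to be expected. This stands: the crude comparison is legitimate description and should stay. What remains is that it cannot support a statement about multifocality independent of other factors, and that no interval is planned around it.

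A reader might infer that the plan commits objectives 2 and 3 to chi-square alone. The documents do not say so. The SAP assigns no test to any objective, and it omits the Kaplan-Meier and Cox methods that the protocol plans, so it is not a complete list. The supportable statement is that no adjusted analysis is specified.

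A reader might also infer that tumour size does confound the result. Neither document reports size by focality or operation by size, and size is not among the correlates of multifocality listed in the Introduction. Confounding is possible, not shown.

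Finally, adjustment has limits here. Factors learned only from the surgical specimen cannot have driven the choice of operation, and Group A focality is itself determined pathologically. HER2 is recorded only if available, and year of surgery is not on the recording list. These points shape the remedy but do not remove the gap.

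**Conclusion.** The concern holds in this form: no adjusted analysis is specified for objectives 2 and 3, and the tests that the SAP lists come with no effect measure or confidence interval. It matters most for objective 3, where separate tests on correlated factors cannot identify which are independently associated with BCT. For objective 2 the crude association is valid description that may be confounded, and a P-value alone does not say how strong it is.

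The size cannot be derived from the documents. On assumed inputs, a size imbalance alone would give a crude OR of 1.14 to 1.68 where the adjusted value is 1.0, and no distortion if the size mix is equal. This shows what could happen, not what is likely. The primary objective is unaffected. The change is worth making because it is cheap and because the study intends to issue recommendations.

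**What to change.** **Objective 3.** Add one parsimonious multivariable logistic model of BCT against mastectomy among Group A multifocal patients. Pre-specify factors known before surgery, such as age, tumour size, clinical nodal status, and biopsy grade and receptors where available. Limit their number by the count of patients in the smaller outcome group. Report ORs with 95% confidence intervals.

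**Objective 2.** Report the crude OR for mastectomy by focality and an OR adjusted by logistic regression for the same kind of factors, each with a 95% confidence interval. Add year of surgery if it can be taken from admission dates.

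**Both.** Keep the contingency tables as description. Leave margin status out, since it is known only after the operation. State how missing receptor and HER2 values will be handled.

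**Cost.** Some SAP wording and a little more analysis, mostly on variables already on the recording list. The downside is that some patients are lost, or a missing category is needed, where receptor or HER2 data are unavailable.
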